	months. SF is measured at screening, baseline, week 2, and thereafter		
	every 4 weeks until week 104 (24 months).		
	 Secondary efficacy endpoint will be assessed by the time to first response of achieving SF ≤ 100 µg/L. 		
Safety assessments	 Key secondary safety endpoint will be ocular safety as measured by incidence of the treatment emergent adverse events. 		
	 Ocular assessments, including visual acuity (ETDRS), slit lamp exam (with LOCS III), tonometry, and fundus examination and photography will be assessed every 6 months. 		
	 Laboratory parameters at screening, baseline, week 2, 4, then every 4 weeks until end of treatment (week 104): 		
	 Hematology, chemistry (including renal and hepatic parameters) and urinalysis 		
	 Coagulation, urine protein/creatinine ratio, transferrin saturation, and SF 		
	 Vital signs at screening, baseline, week 2, 4, then every 4 weeks until end of treatment (week 104) 		
	• ECG and audiometry test at screening, week 24, 52, 76 and 104		
Other assessments	Not applicable		
Data analysis Primary objective:			
	Assess the response rate (RR) of the deferasirox FCT and phlebotomy treatment arms where a response is defined by achieving target SF \leq 100 µg/L on or before month 24. The estimate of the RR and the corresponding 95% CI will be provided for each arm. No formal hypothesis testing is planned in this study. Any patient who discontinues prematurely before meeting the criteria will be considered a non-responder.		
	Key secondary objective:		
	Evaluate ocular safety of deferasirox FCT and phlebotomy over 24 months by the incidence of treatment-emergent ocular AEs (new or worsening from baseline). It will be summarized categorically by system organ class and/or preferred term, overall and by severity, type of AE, and relation to study treatment.		
	No hypothesis will be tested for this key secondary objective.		
	Secondary efficacy objective:		
	Time to first response		
	Response is defined when serum ferritin is $\leq 100 \ \mu$ g/L. For the analysis of time to first serum ferritin $\leq 100 \ \mu$ g/L, the following censoring rule will be applied:		
	 For patients who did not achieve a response, they will be censored at the earliest of the following dates: 		
	Death or discontinuation date due to any reason, or		
	Last SF assessment.		
	Kaplan-Meier estimates will be presented. Median time to response (as well as 25th and 75th percentiles) will be presented along with 95% confidence intervals for the two arms.		

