Increased creatinine ≥ 33% from baseline (average of 2 samples) resulting in creatinine > ULN x 2 consecutive samples (at least 2 weeks apart)	Decrease by 7 mg/kg/day or interrupt if already at 7 mg/kg/day or lower.	
If dose is decreased, but increasing creatinine > ULN	Interrupt treatment.	
After interruption, if creatinine returns to within normal limits on 2 consecutive visits.	Resume 50% of the most recent dose prior to interruption. If after another 4 weeks, creatinine remains stable, resume 100% dose (adjust for weight if needed).	
Creatinine clearance > 40 and < 60 mL/min	Caution in patients if there are additional risk factors that may impair renal function, such as concomitant medications, dehydration, or severe infection.	

Dece medifications for ICL 67052202	
Creatinine clearance < 40 mL/min	Deferasirox must be discontinued.
or increased serum creatinine > 2x age-appropriate ULN	
Urine protein/creatinine ratio	
Any proteinuria	If new or worsening pre-existing proteinuria (assessed by dipstick), collect a urine sample for assessment by the central/local laboratory.
	In case of a single increase of the urinary protein/creatinine ratio, repeat the assessment at the next visit.
> 0.5 urine protein/ creatinine ratio (mg/mg) in two consecutive non-first void urine samples (a minimum of 48h apart), if all other causes of proteinuria have been	Decrease deferasirox by 50%. If UPCR resolves (< 0.5mg/mg) at the next study visit, resume 100% dose.
excluded.	
> 1.0 (mg/mg) in two consecutive non-first void urine	Interrupt deferasirox FCT.
samples (a minimum of 48h apart)	If the increased UPCR resolves (< 0.5 mg/mg) at the next study visit, resume dose at 50% of the last dose. If UPCR remains within normal limits after 4 weeks at the 50% reduced dose, resume study medication at 100% of the last dose.
Persistent proteinuria	If proteinuria persists, discontinue study treatment if the investigator believes it is in the best interest of the patient.
	Novartis may be contacted by the investigator to discuss dosing options.
	Dose adjustment must be based on central/local laboratory results.
Investigations (Hepatic)	
Isolated direct (conjugated) Bilirubin elevation	
> ULN – 1.5 x ULN	Maintain dose
> 1.5 - 3.0 x ULN	Interrupt dosing. Monitor LFTs ^a weekly or more frequently if clinically indicated until resolved to \leq 1.5 x ULN: If resolved \leq 14 days, then maintain dose.
	If resolved > 14 days, then \downarrow 1 dose level (3.5 mg/kg/day FCT)

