7.1.2 Screening

Prior to screening, the patient must give full informed consent on the appropriate form. Once signed and dated by the patient, the investigator must review the study's inclusion and exclusion criteria with the patient to ensure that the patient is eligible to participate.

Two Screening Visits (at -4 weeks and at -2 weeks) are needed to perform key safety parameters prior to first dose administration per the deferasirox drug label and to confirm eligibility criteria.

Molecular testing of HH must be performed at the first screening visit if historical diagnosis is not available.

Specific safety assessments including ophthalmic and audiometry examinations, ECG, and cirrhosis assessment (unless diagnosis is available during the past 12 months, or SF is <1000 μ g/L and AST/ALT are normal) must be performed prior to starting study drug. It is preferred that they are performed at the first screening visit (-4 weeks), but to make it possible for the site to plan the examinations properly, these assessments can be performed at the second screening visit (-2 weeks).

SF, serum creatinine and urine protein/creatinine ratio will be measured at both screening visits and used to assess eligibility. SF should be obtained in the absence of any infection or inflammation.

Serum Pregnancy test will be required for females of child-bearing potential only.

The full list of assessments to be performed during screening is detailed in Table 7-1.

Re-screening is permissible on a case-by-case basis. All assessments at screening visits must be repeated if a patient is re-screened, except for molecular testing of HH, Ocular, Audiometry, ECG, and cirrhosis assessments. Please contact Novartis for guidance and see Section 7.1.2.2 on how to process screen failures.

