7.2.2.6.3 Clinical chemistry

Clinical chemistry samples will be collected at Screening and at subsequent time points as specified in Table 7-1.

Clinical chemistry parameters assessed are listed in Table 7-3.

In accordance with the deferasirox label, serum creatinine, creatinine clearance, alkaline phosphatase, ALT/SGPT, AST/SGOT, direct (conjugated) bilirubin, indirect bilirubin, total bilirubin must be assessed in duplicate before the initiation of therapy to establish a reliable pre-treatment baseline.

FRANCE SPECIFIC ONLY: Serum creatinine and creatinine clearance should be assessed at weeks 2 and 4 after initiation of deferasirox FCT as central lab tests. For patients enrolled in sites in France, serum creatinine and creatinine clearance will also be assessed at weeks 1 and 3 after initiation of deferasirox FCT, and weekly during the first month after dose increases. The assessment is to be performed by the central lab however the local lab may be used. In the clinical database, "Unplanned Central Lab Cover Page" should be used to enter these unscheduled samples information at 'Unplanned' visit, or "Biochemistry Local Unplanned page" will be used in case of local lab assessment. The CRA will obtain the local laboratory reference ranges and a copy of the laboratory certification

Creatinine clearance will be calculated using the Cockcroft-Gault formula every time serum creatinine is collected.

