#### Baseline

Baseline is considered as the result of an investigation describing the 'true' uninfluenced state of the subject.

For **efficacy evaluations**, (e.g. serum ferritin), the last available assessment before or on the date of randomization is taken as 'baseline' value or 'baseline' assessment.

For **safety evaluations** (e.g. laboratory, vital signs, ocular etc.) the last available assessment before or on the date of start of study treatment is taken as 'baseline' value or 'baseline' assessment.

If subjects have no value as defined above, the baseline result will be missing.

If an assessment is planned to be performed prior to the first administration of study treatment in the protocol and the assessment is performed on the same day as the first administration of study treatment, it will be assumed that it was performed prior to study treatment administration if assessment timepoint is not collected or is missing. Unscheduled assessments will be considered in the determination of baseline.

Subjects who start treatment and discontinue from the study on the same day may have 2 different sets of data collected on study Day 1, one being reported to the Day 1 visit, the other reported to the EOT visit. Data reported at the EOT visit are not eligible for baseline selection.

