#### 2.6.7 Laboratory Data

On analyzing laboratory, data from all sources (central and local laboratories) will be combined. The summaries will include all assessments available for the lab parameter collected no later than 30 days after the last study treatment administration date (see Section 2.1.1).

The following summaries will be produced for hematology, urinary, and biochemistry laboratory data (by laboratory parameter and treatment):

- Descriptive Statistics for lab results and change by from baseline time point and treatment arm
- Shift tables using notable/extended ranges to compare baseline to the worst on-treatment value for key lab parameters (see Table 2-1)
- Shift tables using the low/normal/high/(low and high) classification to compare baseline to the worst on-treatment value.
- Trends of key lab parameter values over time (baseline and selected on-treatment timepoints) will be displayed via boxplots based on time windows and corresponding tables displaying the statistics used for the box plots by the selected time points.

The following listings will be produced for the laboratory data:

- Listings of all laboratory data, with classification relative to the laboratory normal range.
- Listing of all lab abnormalities based on notable/extended ranges

Parameter	Criteria
Absolute neutrophils	$< 1.5 \times 10^{9}$ /L (extended range $< 0.5 \times 10^{9}$ /L)
Platelets	$< 100 \times 10^{9}$ /L (extended range $< 50 \times 10^{9}$ /L)
Hemoglobin	< 100 g/L
ALT and AST	$> 5 \times$ ULN and $> 2 \times$ baseline (extended range $> 10 \times$ ULN and $> 2 \times$ baseline)
Total bilirubin	> 2 x ULN
Serum creatinine	> 33% increase from baseline and > ULN at 2 consecutive measurements at least 7 days apart
Creatinine clearance	< 60 mL/min at 2 consecutive measurements at least 7 days apart (extended range < 40 mL/min at least 7 days apart)
Urinary protein/creatinine ratio*	$\geq$ 1.0 mg/mg at 2 consecutive measurements at least 7 days apart

 Table 2-1 Definition of notable/extended ranges for key safety laboratory parameters

Novartis	Confidential	Page 29 of 36
SAP Amendment 1		Study No. CICL670F2203

\* If the unit of the parameter (Urinary protein/creatinine ratio) is in mg/mmol then will have to use a conversion factor as 0.00885 to convert into mg/mg unit for further derivation.

For all analyses, creatinine clearance will be re-derived using the Cockcroft-Gault equation described in Section 5.2.1.

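### The SAP measures the creatinine rise from the last single pre-treatment value, although the protocol takes duplicate samples for a reliable baseline and its dosing table uses the average of two

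*Protocol*

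**What the plan says.** - **Dosing rule.** The serum creatinine row of protocol Table 6-2 (section 6.3.1) reads "Increased creatinine ≥ 33% from baseline (average of 2 samples) resulting in creatinine > ULN x 2 consecutive samples (at least 2 weeks apart"). The rise is thus taken "from baseline (average of 2 samples").
- **Purpose of the duplicates.** Protocol 7.2.2.6.3 says that creatinine, creatinine clearance and named liver tests "must be assessed in duplicate before the initiation of therapy to establish a reliable pre-treatment baseline".
- **Timing of the samples.** Protocol 7.1.2 states that "SF, serum creatinine and urine protein/creatinine ratio will be measured at both screening visits", at weeks -4 and -2. Table 7-1 schedules chemistry again on Day 1, and the protocol summary agrees: "Laboratory parameters at screening, baseline, week 2, 4, then every 4 weeks until end of treatment (week 104"). Three pre-dose values are therefore planned.
- **SAP baseline.** SAP 2.1.1 takes, for all safety evaluations, "the last available assessment before or on the date of start of study treatment". It makes no exception for creatinine.
- **SAP criterion.** Table 2-1 in SAP 2.6.7 flags creatinine at "> 33% increase from baseline and > ULN at 2 consecutive measurements at least 7 days apart". Protocol Table 10-1 has the same criterion and does not say how baseline is formed.
- **Averaging.** SAP 5.2.2 and 5.3.1 average only values reported on the same day. SAP section 4, which lists changes to the protocol's analyses, does not mention the creatinine baseline.

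**The concern.** The protocol collects repeat creatinine so that the baseline does not rest on one reading, and the analysis then rests it on one reading. Error in that value enters every later change for the patient, so one unusually low or high result can create or hide a 33% rise at visit after visit.

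Renal function drives several mandatory dose changes in Table 6-2, and protocol 2.6 reports creatinine elevations in the earlier hemochromatosis study. A reader of the study report is likely to set the notable-creatinine table beside the creatinine-driven dose changes. Differences that come from the definition of baseline could be taken for non-compliance or for a missed signal.

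**Working it through.** The documents give no figure for this point, so there is none to reproduce.

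**1. Noise in the change from baseline.** Let s be the within-person SD of log creatinine, with independent errors, and let m be the number of values averaged for baseline. Approximately:

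SD of log change = s x sqrt(1 + 1/m)

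- m = 1 (SAP): s x sqrt(2) = 1.414 s
- m = 2 (Table 6-2): s x sqrt(1.5) = 1.225 s
- Ratio: sqrt(2/1.5) = 1.155, so the single baseline is 15.5% noisier.

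**2. Effect on the flag, one pair of post-baseline values.** A flag requires both values to exceed 1.33 x baseline and to exceed ULN. The simulation used 400,000 patients per scenario with log-normal error. The CV of 4-8%, the baseline as a fraction of ULN and the true rise are assumptions; the documents give none of them. A false flag is one raised when the true rise is only 25%.

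| Baseline | False flags, last value | False flags, mean of two | Disagreement at a true 40% rise |
|---|---|---|---|
| 0.9 x ULN, CV 4-8% | 5-15% | 2-10% | 15-18% if the last value is one of the two averaged; 27-34% if the two screening values are averaged |
| 0.8 x ULN, CV 6% | 7.4% | 5.7% | 17% or 32%, on the same two readings |
| 0.7 x ULN, CV 4-8% | about 0% | about 0% | 0.2-2.3% over both readings |
| 0.6 x ULN, CV 6% | 0.0% | 0.0% | 0.0% |

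The ULN condition explains the pattern. From 0.7 x ULN, a 25% rise reaches only 0.7 x 1.25 = 0.875 x ULN, and a 40% rise reaches 0.98 x ULN. Most such patients fail the ULN test whichever baseline is used. From 0.9 x ULN, a 25% rise already gives 1.125 x ULN, so the 33% test decides. With no true rise, flags are about nil under both baselines.

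**3. Robustness: ever flagged over 28 post-baseline values.** This run used 60,000 patients per scenario, CV 5-10%, and compared the last value with the mean of the two screening values.

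| True rise | Disagreement, 0.9 x ULN | Disagreement, 0.7 x ULN |
|---|---|---|
| 0% | 0-4% | 0% |
| 25% | 41-44% | 0-4% |
| 33% | about 24% | 1-13% |
| 50% | 0.1-2.5% | 0.1-2.5% |

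Repeated visits enlarge the effect near the threshold, but its location is much the same. The 4% (no rise) and 13% (0.7 x ULN) figures arise at CV 10%. Individual classification moves more than the total. At 0.9 x ULN, CV 7.5% and a 25% rise, 56.3% are flagged with the mean and 55.6% with the last value, yet 43.9% of patients are classified differently.

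**4. Which two samples.** Table 6-2 does not say which two of the three scheduled pre-dose values are averaged. In the same run, averaging the two screening values or the second screening and Day 1 values changed up to 28% of near-threshold classifications.

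**5. Other differences between the two criteria.**

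| Element | Table 6-2 | SAP Table 2-1 and protocol Table 10-1 |
|---|---|---|
| Rise | at least 33% | more than 33% |
| Spacing of the two samples | at least 2 weeks | at least 7 days |

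Protocol 7.1 allows 3 days either side at Weeks 2 and 4, so the gap between these visits runs from 8 to 20 days. If each visit falls uniformly on one of the 7 allowed days, the gap is under 14 days in 21 of 49 combinations, or 43%. Such a pair meets the SAP spacing but not that of Table 6-2, whatever the baseline.

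**The case against.** The last value before treatment is one pre-specified rule, applied alike to all safety data in both arms. The analysis is descriptive, and the creatinine table supports neither the primary nor the key secondary endpoint. All laboratory data are listed, so an averaged baseline could be recomputed. Neither document says that Table 2-1 should reproduce the dosing rule. SAP 2.3.1 summarises dose changes from case report form fields, and Table 6-2 applies to deferasirox only, while Table 2-1 covers both arms. All of this stands, and it keeps the point small.

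It also rules out four stronger readings that a reader might infer:

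- **That the table will fail to match dose changes.** The documents support only that it may, mainly near the threshold and near ULN.
- **That any mismatch comes from the baseline alone.** Spacing and inequality differ as well, and those differences already exist between Tables 6-2 and 10-1 of the protocol.
- **That the SAP throws away one of two samples.** Three pre-dose samples are scheduled, and Table 6-2 does not name its two.
- **That Table 6-2 supports averaging the liver tests or creatinine clearance.** It specifies an average for serum creatinine only. Its liver rows refer simply to baseline, and its creatinine clearance rows use absolute limits.

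What the objection does not answer is why samples required for a reliable baseline are not combined in the analysis baseline. No SAP rule averages across days.

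**Conclusion.** The point holds as a minor improvement. The SAP baseline for creatinine differs from the only baseline definition that the protocol gives for creatinine, and it is noisier: 15.5% in the SD of the log change, assuming independent errors.

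The practical effect depends on assumed values. It matters for patients with a true rise near 33% who start at about 0.8 x ULN or higher. It is close to nil with no true rise, and small for a baseline of 0.7 x ULN or lower unless the within-person CV approaches 10%. The documents give neither the CV nor the distribution of baseline creatinine, so the number of patients affected in this trial cannot be stated. Changing the baseline would reduce noise, but would not by itself bring Table 2-1 into line with Table 6-2.

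**What to change.** 1. In SAP 2.1.1, define baseline serum creatinine, and the creatinine clearance derived from it, as the mean of named pre-treatment samples, or the single value where only one exists. Name the visits.
2. Keep the last-value baseline as a sensitivity version of the notable-creatinine table.
3. Optionally treat the other duplicate parameters in protocol 7.2.2.6.3 in the same way. The basis is that section, not Table 6-2.
4. State that SAP Table 2-1 is a reporting criterion and not the dosing rule.
5. Reconcile protocol Table 6-2, section 7.2.2.6.3 and Table 10-1 with SAP 2.1.1 and Table 2-1, including which two samples Table 6-2 averages. This review takes no view on which dosing rule is right.

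The cost is a few SAP sentences and one extra table. The samples are already scheduled. The downside is that creatinine would depart from the uniform last-value rule used for the other safety data.

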6.3 Dose modifications

6.3.1 Dose modification and dose delay

For patients who do not tolerate the protocol-specified dosing schedule, dose interruptions and/or reductions are either recommended or mandated in order to allow patients to continue the study treatment of defension FCT.

These dose modifications are summarized in Table 6-2. Deviations from the mandatory dose interruptions and/or reductions are not allowed. Permanent treatment discontinuation of deferasirox FCT is mandatory for specific events indicated in Table 6-2 or listed in Section 7.1.5.

These dose changes must be recorded on the Dosage Administration Record eCRF. It is important to keep an accurate dose adjustment records to enable an adequate evaluation of exposure.

Phlebotomy will be conducted at a frequency determined by the treating physician's clinical judgement for optimal iron control. The name of the facility, the date of phlebotomy, hematocrit level prior to phlebotomy and amount of blood withdrawn must be captured in Phlebotomy Record and local lab eCRFs. Phlebotomy must be interrupted when SF $\leq 100 \mu g/L$ and may be resumed when SF $\geq 100 \mu g/L$.

Novartis Amended Protocol Version 01 (Clean)

Table 6-2 Criteria for dose reduction / interruption and re-initiation of deferasirox FCT

Dose modifications for ICL670F2203		
Serum Ferritin (SF)		
After an initial starting dose (7 mg/kg/day) for 3 months (12 weeks), dose may be adjusted based on SF level. Dose increase cannot be more than 3.5 mg/kg/day at each adjustment.		
<300 µg/L	Decrease to 3.5 mg/kg/day	
300-1000 μg/L	Maintain 7 mg/kg/day	
>1000-2000 µg/L	Increase to 10.5 mg/kg/day	
>2000 µg/L	Increase to 14 mg/kg/day (higher doses are not allowed.)	
SF ≤ 100 μg/L at any time	Interrupt deferasirox FCT	
SF \geq 300 µg/L after dose interruption	Re-initiate deferasirox FCT 3.5 mg/kg/day. If SF continues to increase, increase to 7 mg/kg/day (maximum dose for maintenance phase).	
Body Weight		
Increase/decrease if weight changes >10% compared to baseline weight or weight at last dose adjustment due to a change in weight	Dose of study medication will be adapted using Dosing Table (provided in Appendix 14.1) When weight changes >10% compared to baseline weight or weight at last dose adjustment due to a change in weight, re-calculate dose. Smaller variations in weight (<10%) do not require dose adjustments.	
Investigations (Renal)		
Serum creatinine		
Single increase	Maintain dose and repeat assessment at next visit.	

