Dose modification criteria for auditory and ocular disturbances		
Auditory (decreased hearing) and ocular (lens opacities)	Auditory and ophthalmic testing (including funduscopy) is required before starting deferasirox.	
disturbances have been reported with deferasirox.	If disturbances are noted, consider reducing the dose or interruption. Repeat testing may be done per investigator's judgement.	

Dose modifications for ICL670F2203		
Dose modification criteria for hypersensitivity reactions		
Cases of serious hypersensitivity reactions, such as anaphylaxis and angioedema, have been reported in patients receiving deferasirox. In the majority of cases, onset of the reaction occurred within the first month of treatment.	If reactions are severe, discontinue deferasirox and institute appropriate medical intervention. Due to the risk of anaphylactic shock, do not reintroduce deferasirox in patients who have experienced previous hypersensitivity reactions.	
Dose modification criteria for cytopenias		
Unexpected Cytopenias	Post-marketing reports (both spontaneous and from clinical trials) of cytopenias occurred mostly in patients with pre-existing hematological disorders and were frequently associated with bone marrow failure. Their relationship with deferasirox was uncertain. The standard clinical management of such hematological disorders is regular monitoring of complete blood count. Consider interrupting deferasirox for unexplained cytopenia. Consider reintroducing deferasirox once the cause of cytopenia is identified.	
Gastrointestinal disturbances		
Diarrhea, constipation, nausea, vomiting and abdominal pain.	At the first sign of diarrhea**, consider an anti-diarrheal medication, such as loperamide. Discontinue any laxative or stool softener and eat small, frequent meals.	
	If appropriate, maintain adequate hydration with approximately 8 glasses of water per day. If the gastrointestinal issues (diarrhea, constipation, nausea, vomiting and abdominal pain) persist, discontinue study drug if the investigator believes that is in the best interest of the patient.	
All dose modifications should be based on the worst preceding toxicity.		
a. Core LFTs consist of ALT, AST, GGT, total bilirubin (fractionated [direct and indirect] if total bilirubin > 2.0 x ULN), and alkaline phosphatase (fractionated [quantification of isoforms], if alkaline phosphatase > 2.0 x ULN.)		

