"Combined" defined as total bilirubin increase to the defined threshold concurrently with ALI/ASI increase to the defined threshold		

If combined elevations of AST or ALT and total bilirubin do not meet the defined thresholds, please follow the instructions for isolated elevation of total bilirubin and isolated elevation of AST/ALT, and take conservative action based on the degree of the elevations (e.g. discontinue treatment at the situation when omit dose is needed for one parameter and discontinue treatment is required for another parameter). After all elevations resolve to the defined thresholds that allow treatment re-initiation, restart treatment either at the same dose or at one dose lower if criterion is met for dose reduction.

^{c.} "Cholestasis" defined as alkaline phosphatase elevation (> 2.0 x ULN and R < 2) in patients.

* Note: If total bilirubin > 3.0 x ULN is due to the indirect (non-conjugated) component only, and hemolysis as the etiology has been ruled out as per institutional guidelines (e.g., review of peripheral blood smear and haptoglobin determination), then \downarrow 1 dose and continue treatment at the discretion of the investigator.

** Note: anti-diarrheal medication is recommended at the first sign of abdominal cramping, loose stools or overt diarrhea.

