6.3.3.1 Follow up on potential drug-induced liver injury (DILI) cases

Increases in ALT and AST with an elevated total bilirubin can be seen in advanced stage HH, but is uncommon.

Increases in ALT and AST with an increased total bilirubin may be indicative of a potential DILI and should be considered as a clinically important event.

The threshold for potential DILI may depend on the patient's baseline AST/ALT and total bilirubin value; patients meeting any of the following criteria will require further follow-up as outlined below:

- Baseline normal ALT and AST and total bilirubin: AST or ALT > 3.0 x ULN combined with total bilirubin > 2.0 x ULN
- Elevated baseline AST or ALT or total bilirubin: [AST or ALT > 2 x baseline AND > 3.0 x ULN] OR [AST or ALT > 8.0 x ULN] combined with [total bilirubin > 2 x baseline AND > 2.0 x ULN]
- Normal ALT and AST with increased total bilirubin: rule out Gilbert's syndrome, defined by increased indirect bilirubin.

Medical review needs to ensure that liver test elevations are not caused by cholestasis, defined as alkaline phosphatase > 2.0 x ULN with R < 2 in patients.

Note: (R is calculated by ALT divided by alkaline phosphatase, using multiples of the ULN for both values. It denotes whether the relative pattern of ALT and/or alkaline phosphatase elevation is due to cholestatic ($R \le 2$), hepatocellular ($R \ge 5$), or mixed (R > 2 and < 5) liver injury.

In the absence of cholestasis, patients must immediately discontinue from study treatment and repeat LFTs as soon as possible, preferably within 48 hours from the awareness of abnormal results. Evaluation should include laboratory tests, detailed history, physical assessment and consideration of liver metastasis or new liver lesions, obstructions/compressions, etc.

1. Laboratory tests should include ALT, AST, albumin, creatinine kinase, total bilirubin, direct and indirect bilirubin, GGT, prothrombin time/INR and alkaline phosphatase.

Confidential

- 2. Collect detailed history, such as review of ethanol, concomitant medications, herbal remedies, supplement consumption, pre-existing liver conditions or risk factors.
- 3. Testing for acute hepatitis A, B, C or E infections and liver imaging (e.g. biliary tract) if warranted.
- 4. Additional testing for other hepatotropic viral infections (CMV, EBV or HSV), autoimmune hepatitis or consultation with a hepatologist for liver biopsy if clinically indicated.

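### Table 6-2's isolated-bilirubin rows are headed direct bilirubin but its notes refer to total, and the weekly liver panel need not include the direct value that decides the 14-day rule

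*Protocol*

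**What the plan says.** All of this is in Protocol Section 6.3.1, Table 6-2 (hepatic investigations), unless stated otherwise.

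- **Heading.** The bilirubin rows (> ULN-1.5, > 1.5-3, > 3-10 and > 10 x ULN) stand under "Isolated direct (conjugated) Bilirubin elevation". There is no separate set for total bilirubin.
- **Actions.** In the > 1.5-3 row, dosing is interrupted. The dose is kept if the value falls to at most 1.5 x ULN within 14 days and drops one level if it takes longer. In the > 3-10 row, resolution within 14 days means one level lower, and later resolution means permanent discontinuation. Both rows use weekly liver tests marked with footnote a.
- **Footnote a.** The core liver tests include "total bilirubin (fractionated [direct and indirect] if total bilirubin > 2.0 x ULN".
- **Footnote b.** For combined elevations below the combined thresholds: "please follow the instructions for isolated elevation of total bilirubin and isolated elevation of AST/ALT".
- **\* note, on the two upper rows.** It applies when total bilirubin > 3 x ULN "is due to the indirect (non-conjugated) component only" and "hemolysis as the etiology has been ruled out as per institutional guidelines". The dose then goes down one step, and sites may "continue treatment at the discretion of the investigator".
- **Force of the table.** "Deviations from the mandatory dose interruptions and/or reductions are not allowed".

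**The concern.** A mandatory dosing rule should name one analyte and require that it be measured. This one fails on both counts. The heading names direct bilirubin, while footnote b and the * note speak of total. A purely indirect rise would not put a patient in a direct-bilirubin row, so the * note hangs on rows for a different analyte. The liver tests specified for the 14-day decision may also come back without a direct value.

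The decision has real consequences. It separates keeping from reducing the dose, where one level is 3.5 mg/kg/day, or half (3.5/7) of the starting dose. In the higher row it separates reduction from permanent discontinuation. A patient who discontinues before reaching the ferritin target counts as a non-responder (Protocol 10.4.3, SAP 2.4.3).

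Indirect-only elevations are foreseeable. Protocol 6.3.3.1 lists "Normal ALT and AST with increased total bilirubin" as a reason to rule out Gilbert's syndrome. Section 5.3 excludes total bilirubin > 1.5 x ULN only when both screening samples show it.

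**Working it through.** The plan gives no figure to reproduce. The check compares the texts and then does arithmetic on assumed reference limits.

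**1. The two analytes can give different actions, with no assumed limits.** Take a patient with normal baseline values, then ALT 4 x ULN and total bilirubin 1.8 x ULN, with the rise entirely indirect. The combined threshold (total > 2 x ULN) is not met, so footnote b applies.
- Read as total: 1.8 falls in the > 1.5-3 row, so interrupt.
- Read as direct: no bilirubin row applies, and the ALT > 3-5 x ULN row says keep the dose and repeat the tests.
- At 1.8 x ULN footnote a does not require fractionation, so the site may lack the value that separates the two readings.

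**2. Can the direct value be missing on day 14?** Assumed limits, not in the documents: total ULN 20 µmol/L (range 17-21), direct ULN 5 (range 3.4-7).

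| | Value (µmol/L) | x ULN over the range | Reading |
|---|---|---|---|
| Start, direct | 22 | 22/7 = 3.1 to 22/3.4 = 6.5 | > 3-10 row, interrupt |
| Start, total | 32 | 32/21 = 1.5 to 32/17 = 1.9 | not > 2, direct not required |
| Day 14, total | 20 | 20/21 = 0.95 to 20/17 = 1.2 | direct not required |
| Day 14, if direct is 5 | 5 | 5/7 = 0.7 to 5/3.4 = 1.5 (1.47) | resolved, one level lower |
| Day 14, if direct is 12 | 12 | 12/7 = 1.7 to 12/3.4 = 3.5 | not resolved, discontinue |

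The same total of 20 fits both outcomes, with indirect 15 or 8.

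**3. When would footnote a require the direct value?**
- Direct alone lifts total above 2 x its ULN only when direct exceeds 40/5 = 8 x its own ULN (34/7 = 4.9 to 42/3.4 = 12.4).
- At the resolution limit, direct is 1.5 x 5 = 7.5, or 7.5/20 = 0.38 x the total ULN (5.1/21 = 0.24 to 10.5/17 = 0.62). Footnote a then requires fractionation only if indirect exceeds 2 - 0.38 = 1.6 x the total ULN (1.4 to 1.8).
- A second set of assumptions agrees. Let the direct ULN be 20-40% of the total ULN, and direct 30-80% of total. Total at the resolution limit is 1.5 x (ULN ratio)/(direct share), which runs from 1.5 x 0.2/0.8 = 0.38 to 1.5 x 0.4/0.3 = 2.0 x ULN. It never exceeds the trigger.

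**4. Do scheduled visits fill the gap?** Table 7-3's central chemistry list includes direct bilirubin. Scheduled visits are 14 days apart up to Week 4 and 28 days apart afterwards, so 25 of 27 nominal intervals exceed 14 days. With the ±7-day windows, monthly gaps run from 14 to 42 days. The scheduled panel cannot be relied on for a 14-day decision.

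**5. Would retitling the rows to total be enough?** No. An indirect-only total of 45 (45/21 = 2.1 to 45/17 = 2.6 x ULN) would be interrupted. A total of 64 (64/21 = 3.0 to 64/17 = 3.8 x ULN) with hemolysis ruled out could continue one level lower under the * note. The milder elevation would get the stricter action.

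**The case against.** The best defence is that a sensible site would reach the right answer.

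- Under a direct-bilirubin heading, resolution naturally means direct bilirubin, and footnote a describes a core panel, not its limit.
- Section 6.3.3 requires at least weekly follow-up for four weeks after an interruption for an abnormal value. Section 8.1.2.1 requires laboratory abnormalities that count as adverse events to be followed until resolved or explained.
- Section 7.2.2.6 sends nearly all specimens to a central laboratory whose chemistry list includes direct bilirubin, and asks for a parallel central sample when a local test is used.
- Footnote b can only point to the one set of rows that exists, and the * note states its own trigger, condition and action.
- The examples use assumed limits and chosen values and give no frequency. Cirrhosis and active hepatitis B or C are excluded at entry.

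Part of this stands. Sites may order direct bilirubin, the * note can be read on its own, and the Central Laboratory Manual, which may fix the content of unscheduled draws, is not available here. The likelihood of a wrong action is not estimated. Following total bilirubin after permanent discontinuation is not an error.

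The defect remains. None of the cited provisions names the analyte for the weekly checks, and none reconciles footnote b with the heading. Having a single destination for footnote b does not tell a site which value to compare with the bands, as step 1 of the working shows.

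**Conclusion.** The concern holds. The table contradicts itself on the analyte for a mandatory interrupt, reduce or discontinue rule, and the weekly panel it specifies does not guarantee the value that decides the outcome. The analyte conflict rests on the text alone. The monitoring gap follows from footnote a, and the size of the examples rests on the assumed reference limits, though every example gives the same action across the stated ranges.

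The reach is limited to the deferasirox arm and probably to few patients. The primary endpoint definition, the sample size and the planned analyses are unchanged. It should still be fixed, because it alters operative dosing instructions and not merely their presentation.

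**What to change.** Keep direct bilirubin as the governing analyte. This fits the heading and Section 7.2.2.6.3, which already requires duplicate pre-treatment direct bilirubin.

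1. Amend footnote a so that direct bilirubin is reported at every weekly check during an interruption under these rows, whatever the total.
2. Make footnote b point to isolated elevation of direct bilirubin.
3. Move the * note to its own row for total bilirubin > 3 x ULN from the indirect component only, keeping the hemolysis condition and the investigator's discretion.

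Monitoring of total bilirubin after permanent discontinuation can stay. If the sponsor's clinicians prefer total bilirubin throughout, the * note's relief must also cover indirect-only elevations of > 1.5-3 x ULN, for the reason in step 5 of the working.

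The cost is amendment wording in one table and one more analyte on blood already drawn weekly.
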